5.4.4.2. Vital Signs and Physical Examination Findings

Continuous vital sign parameters including pulse, blood pressure (systolic and diastolic), and weight will be summarized at each assessment time point. The observed value and change from baseline will be summarized by intervention group. Descriptive statistics (mean, standard deviation, median, minimum and maximum) will be presented.

Incidence of markedly abnormal vital signs during intervention, as defined in [Table 15](#), will be summarized for participants who had a baseline assessment and at least 1 postbaseline assessment for that vital sign. A listing of participants with markedly abnormal vital signs will be presented.

Table 15: Markedly Abnormal Vital Signs

Vital Sign	Criteria
Pulse	>120 bpm and with >30 bpm increase from baseline
	<50 bpm and with >20 bpm decrease from baseline
Systolic blood pressure	>180 mm Hg and with >40 mm Hg increase from baseline
	<90 mm Hg and with >30 mm Hg decrease from baseline

Table 15: Markedly Abnormal Vital Signs

Vital Sign	Criteria
Diastolic blood pressure	>105 mm Hg and with >30 mm Hg increase from baseline
	<50 mm Hg and with >20 mm Hg decrease from baseline

5.4.4.3. Electrocardiogram

No analysis is planned.

5.4.4.4. Other Safety Parameters**5.4.4.4.1. Suicidal Ideation and Behavior**

The electronic Columbia-Suicide Severity Rating Scale (eC-SSRS) will be used as a screening tool to prospectively evaluate the potential of guselkumab to induce suicidal ideation and behavior. The eC-SSRS defines five subtypes of suicidal ideation and behavior in addition to self-injurious behavior with no suicidal intent, and is a fully-structured participant self-report questionnaire, including standardized questions, follow-up prompts, error handling routines, and scoring conventions (Mundt 2013) (Posner 2011). Two versions of the eC-SSRS will be used in this study, the Lifetime version and the Since Last Contact version. The Lifetime version will be conducted during the screening visit and the Since Last Contact version will be conducted at all other visits through Week 168.

Participants will complete the eC-SSRS questionnaire using the Sponsor-provided electronic tablets (or through an Interactive Voice Response System, if available). Study site personnel will train the participants on how to use the electronic device and/or a telephone system. The eC-SSRS will be provided in the local languages in accordance with local guidelines.

The eC-SSRS will be performed during each evaluation visit according to the Time and Events schedule. The eC-SSRS should be performed after the joint assessment at the screening visit (after signing informed consent). At Week 0/baseline and at all post-baseline visits, the eC-SSRS will be the first assessment/questionnaire that the participant completes prior to study intervention administration.

CCI

- [REDACTED]
- [REDACTED]
- [REDACTED]
- [REDACTED]
- [REDACTED]
- [REDACTED]

Negative suicidality indication reports are generated from the eC-SSRS vendor when there are NO indications of the above.

Any eC-SSRS findings, which in the opinion of the investigator are new or considered to be a worsening and clinically significant, should be reported on the AE eCRF.

CCI

5.5. Other Analyses

5.5.1. Pharmacokinetics

PK analyses will be performed on the PK analysis set, defined as participants who have received at least 1 complete dose of guselkumab and have at least 1 valid blood sample drawn for PK analysis (Section 4.7). Subjects will be analyzed according to the treatment groups that they actually receive. No imputation for missing concentration data will be performed.

Descriptive statistics (N, mean, SD, median, range, CV (%) and IQ range) will be used to summarize serum guselkumab concentrations at each sampling time point by treatment group. PK data may be displayed graphically. The following analyses will be performed by treatment group as appropriate:

- Summary of serum guselkumab concentrations at each visit by treatment group

- Proportion of subjects without detectable serum guselkumab concentration at each visit by treatment group
- Summary of serum guselkumab concentrations at each visit by treatment group and body weight
- Summary of serum guselkumab concentrations at each visit by treatment group and baseline MTX use (Yes, No)
- Summary of serum guselkumab concentrations by baseline CRP levels
- Plot of median (IQ) serum guselkumab concentrations over time by treatment group

In addition, the relationship between serum guselkumab concentrations and safety or efficacy may be explored.

For summary statistics of serum guselkumab concentrations, concentration values below the lower limit of quantification will be treated as zero. Once a subject meets one of the following dosing deviation criteria, the subject's data will be excluded from the by-visit data analyses from that point onwards.

Dosing deviation criteria:

- Discontinue SC guselkumab administrations.
- Skipped an SC guselkumab administration.
- Received an incomplete/ incorrect SC dose.
- Received an incorrect SC study agent.
- Received an additional SC guselkumab dose.

In addition, if a subject has an administration outside of visit windows (Section 5.1.1), the concentration data collected at and after that visit will be excluded from the by-visit data analyses. Additional exclusions for incongruous PK data to be implemented based on Janssen SOP-07948.

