## Study Phases and Duration of Treatment

There will be 5 phases in this study: Screening, double-blind placebo-controlled, double-blind active treatment, LTE and safety follow-up.

- The screening phase of up to 6 weeks will allow for sufficient time to perform screening study evaluations and determine study eligibility.
- The second phase of the study will be the double-blind, placebo-controlled phase from Week 0 to Week 24. The primary endpoint will be evaluated at Week 24.
- The third phase of the study will be the double-blind, active treatment phase from Week 24 through Week 48. This duration will provide adequate time to evaluate the maintenance of efficacy and long-term safety of guselkumab in PsA over a 48-week exposure period.
- The fourth phase of the study will be the LTE from Week 48 through Week 156.
- The final phase of the study will be the safety follow-up phase and will be 12 weeks from the last administration of study intervention to the final safety visit (whether in the core study or LTE). The safety follow-up period allows for monitoring of participants for a period equivalent to approximately 5 times the half-life of guselkumab.

The placebo-controlled period is limited to 24 weeks. An EE option is included in the study design to provide additional treatment options for participants who have <20% improvement in swollen and tender joint counts at Week 16.

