#### **6.4. Study Intervention Compliance**

When participants self-administer study intervention at home, compliance with study intervention will be assessed at each visit. Compliance will be assessed by direct questioning during the site visits and documented in the source documents and eCRF. Deviation(s) from the prescribed dosage regimen must be recorded in the eCRF.

Participants will receive instructions on compliance with study treatment when they begin self-administration of study intervention at home. When participants begin self-administration at home, the investigator or designated study personnel will maintain a log of all study intervention dispensed and returned.

When study intervention is self-administered by participants at home, participants will record all study intervention administrations on a diary card.

During the study, the investigator or designated study research personnel will be responsible for providing additional instruction to reeducate any participant who is not compliant with taking the study intervention.

Compliance with the treatment schedule is strongly encouraged. It is understood that treatment may be interrupted for health-related or safety reasons. Therefore, if for any reason a participant cannot receive a dose of study intervention at the scheduled visit, the participant must make every effort to still come in for the scheduled assessments for that visit. The dose should be administered within 2 weeks of that scheduled visit. Study intervention administrations must be at least 14 days apart. The participant should then resume the normal study schedule relative to the baseline visit (Week 0). In the case when a participant does not come into the investigational site for a scheduled visit, the site will follow-up with that participant. Due diligence could include telephone calls, certified letters, and email requests. Measures taken to obtain follow-up information must be documented.

Study-site personnel will keep a log of all study intervention dispensed and will compare the amount of study intervention dispensed with the amount returned.

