- **NP:** [(CRP<5.7 and ERN<=5) OR (CRP<5.7 and 5<ERN<16 and COR=Yes)] AND (R_DIFF_ERN = No)
- **LMP:** [Other] AND (R_DIFF_ERN = No)

With the abbreviations standing for:

COR = the participant's baseline oral corticosteroid use

ERN = the participant's baseline number of joints with erosion

R_DIFF_ERN = (Yes/No) if the absolute reader difference for number of joints with erosions at baseline was >8

CRP = the participant's most recent screening CRP Level in mg/dL

Group I (n=350)

Participants will receive SC guselkumab 100 mg at Weeks 0, 4, 12, 20, 28, 36 and 44 and placebo at Weeks 8, 16, 24, 32, 40 and 48 to maintain the blind.

Group II (n = 250)

Participants will receive SC guselkumab 100 mg at Weeks 0, 4, 8, 12, 16, 20, 24, 28, 32, 36, 40, 44 and 48.

Group III (n=350)

[figure not shown]
Participants will receive SC placebo at Weeks 0, 4, 8, 12, 16 and 20, and will cross over at Week 24 to receive SC guselkumab 100 mg at Weeks 24, 28, 32, 36, 40, 44 and 48.

At Week 16, all participants in Groups I II and III with < 20% improvement from baseline in both tender and swollen joint counts will qualify for early escape (EE) and will be allowed to initiate or increase the dose of one of the permitted concomitant medications up to the maximum allowed dose as specified in [Table 2](#), as selected by the investigator.

The core study lasts from Screening to Week 48. At Week 48, participants who have not discontinued will be eligible to enter a long-term extension (LTE) for a period of up to approximately two years (ie, Week 48 through Week 156) where they will continue on the same treatment regimen.

Database locks (DBLs) are scheduled at Weeks 24, 48, 96 and end of study (Week 168). The first DBL will occur when all randomized participants have either completed the Week 24 assessments or terminated study participation prior to the Week 24 visit (referred to as Week-24 DBL). The second DBL will occur when all randomized participants have either completed the Week 48 assessments or terminated study participation prior to the Week 48 visit (referred to as Week-48 DBL). The third DBL will occur when all randomized participants have either completed the Week 96 assessments or terminated study participation prior to the Week 96 visit (referred to as Week-96 DBL). The fourth and final DBL will occur when all randomized participants have either completed their final safety visit or have terminated study participation.

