5.1.1.1. Visit Windows for Dosing and PK Analysis

All post-baseline visits from Baseline through Week 24 will have a visit window of \pm 4 days, and from Week 28 through Week 156 will have a visit window of \pm 1 week (7 days). The final safety follow-up at Week 168 will have a visit window of \pm 2 weeks (14 days). This information will be used to identify out-of-window dosing or visits (non-radiographic).

For PK analyses, if a participant has an administration outside the visit window at a visit, the concentration data collected at and after that visit will be excluded from the by-visit data analyses.

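### The PK by-visit exclusion for out-of-window injections is not limited to guselkumab, so a late placebo injection can drop concentrations it cannot have affected

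*SAP*

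**What the plan says.** The rule appears twice in the SAP, each time for the by-visit analyses. Section 5.5.1 has it as "if a subject has an administration outside of visit windows (Section 5.1.1), the concentration data collected at and after that visit will be excluded". The wording in Section 5.1.1.1 is "if a participant has an administration outside the visit window at a visit, the concentration data collected at and after that visit will be excluded". The windows in 5.1.1.1 are ±4 days through Week 24 and ±7 days from Week 28 to Week 156.

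Just above the rule, SAP 5.5.1 lists five dosing deviations that also end a participant's contribution to the by-visit analyses. Three of them (discontinued, skipped, additional dose) are written for guselkumab by name. The out-of-window rule is not, and neither section says when a participant may return.

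Many injections are placebo. SAP 1.2 gives Group I "placebo at Weeks 8, 16, 24, 32, 40 and 48 to maintain the blind", and Group III receives only placebo until it crosses over at Week 24. On a dose that cannot be given at its visit, Protocol 6.4 says: "The dose should be administered within 2 weeks of that scheduled visit".

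**The concern.** A late guselkumab dose changes the concentrations that follow it, so a summary at nominal visits has reason to set those samples aside. A late placebo injection changes nothing. As worded, the rule treats the two alike. A Group III participant whose Week 8 placebo injection was 5 days late would lose every guselkumab concentration after crossover from the by-visit tables and plots. Had the same participant skipped that injection, the skipped-dose criterion would not have applied, because it names guselkumab.

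Serum guselkumab concentration is a stated other-secondary endpoint. The summaries affected are those by visit, body weight, methotrexate use and CRP, and the proportion without detectable drug. The loss would fall on the two arms that receive placebo and not on the q4w arm.

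**Working it through.** The plan gives no retention figure and no deviation rate, so there is nothing to reproduce. The check has four steps.

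**1. Placebo injections at scheduled visits.** The Schedule of Activities has visits at Weeks 4, 8, 12, 16, 20, 24, 28, 36 and 48. Week 0 is the anchor and cannot be out of window.
- Group III, before crossover: Weeks 4, 8, 12, 16 and 20, so k = 5.
- Group I, through Week 24: Weeks 8, 16 and 24, so k = 3.

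All of these are visits, so the phrase *at a visit* in 5.1.1.1 does not spare them.

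**2. Share removed by placebo timing alone.** Let q be the chance that one injection is out of window. It is assumed, and taken as independent between injections. Share removed = 1 − (1 − q)^k. If exclusion is unrelated to concentration, the standard error of a Group III mean grows by 1/√(1 − share).

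| q | Group III, 1 − (1 − q)^5 | of 350 planned | SE factor | Group I after Week 24, 1 − (1 − q)^3 |
|---|---|---|---|---|
| 1% | 4.9% | 17 | 1/√0.951 = 1.03 | 3.0% |
| 2% | 9.6% | 34 | 1/√0.904 = 1.05 | 5.9% |
| 5% | 22.6% | 79 | 1/√0.774 = 1.14 | 14.3% |

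**3. What a late injection does to later troughs.** Protocol 4.2 describes the 12-week follow-up as "a period equivalent to approximately 5 times the half-life of guselkumab", so the half-life is about 84/5 = 16.8 days. The calculation uses a one-compartment bolus approximation, which is an assumption. For q4w dosing, f = 2^(−28/16.8) = 0.315 and the steady-state trough, in units of one dose, is f/(1 − f) = 0.460. A dose L days late shifts the next trough by [2^(−(28 − L)/16.8) − f]/0.460, and each later trough by a further factor f.
- L = 5: (0.387 − 0.315)/0.460 = about 16%, then 5%, then 2%.
- L = 14: (0.561 − 0.315)/0.460 = about 54%, then 17%, 5% and 2%.
- Placebo, any L: 0%.

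The first troughs after a late guselkumab dose are materially off schedule. After a late placebo injection none is.

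**4. Whether injections between visits count.** Section 5.1.1.1 ties the trigger to a visit and 5.5.1 does not. Before the Week 48 sample there are 11 post-baseline q4w injections, 8 of them at scheduled visits. Counting guselkumab and placebo together, 1 − (1 − q)^11 gives 10%, 20% and 43% excluded at q = 1%, 2% and 5%. Using 8 injections gives 8%, 15% and 34%. Two programmers could follow the SAP and produce different tables.

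**The case against.** The strongest reply is that the context already settles the matter. The rule sits in a guselkumab PK section, beneath criteria that mostly name guselkumab, and a pharmacokineticist would probably read *administration* that way. The section also defers further exclusions to an internal procedure that the documents do not reproduce. That makes the literal reading less likely to be applied. It does not change the words, which are unqualified in both places.

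Several limits stand in full:
- The exclusion covers by-visit analyses only. Samples before the deviation remain, Protocol 9.4.5 foresees a concentration listing and separate population PK modelling, and no such exclusion is stated for either. A reader might infer that valid data are lost for good. The documents do not say so.
- For guselkumab doses some exclusion is sensible: a 14-day delay moves the next q4w trough by about half. How long to exclude is a choice on which pharmacokineticists may differ.
- A reader might project losses of half or more late in the extension. That needs every q4w injection to count, including home injections, and independent deviations. For the q8w arm it also needs placebo to continue after the Week-48 database lock, when it is no longer required. Deviations that cluster within participants would lower the share ever excluded.
- A reader might infer that compliant dosing is penalised. The 2-week allowance is a contingency. Protocol 6.4 asks for Sponsor consultation on out-of-window visits, and SAP Appendix 3 still classes out-of-window treatment as a deviation.

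**Conclusion.** The point holds in a limited form. Taken literally, SAP 5.1.1.1 and 5.5.1 let a late placebo injection remove later guselkumab concentrations from the by-visit PK summaries, with no re-entry and no pharmacological reason. On assumed, independent rates of 1%, 2% or 5% per injection, that is about 5%, 10% or 23% of Group III for all post-crossover summaries. The true rate cannot be learned from the documents.

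The demonstrable cost is precision: standard errors about 3%, 5% or 14% wider in Group III at those rates. A reader might go further and conclude that the late summaries are biased or describe only perfect attenders. Nothing in the documents links visit timing to exposure, the windows tolerate 4 or 7 days either way, and N is reported at each time point, so shrinkage would be visible. These summaries are descriptive; no hypothesis test or primary conclusion depends on them.

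**What to change.** In SAP 5.1.1.1 and 5.5.1:
1. Change the trigger from *an administration* to *a guselkumab administration*.
2. State whether injections given between scheduled visits count, and use the same wording in both sections.
3. Report the number of participants excluded at each visit, by arm.

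Optionally, add a supportive by-visit summary that re-admits samples once the deviation has washed out, for example after 12 weeks, the protocol's approximate five half-lives. After a 14-day delay the carry-over in a q4w trough would by then be about 5%. The SAP dosing window and the 2-week allowance in Protocol 6.4 should also be reconciled for the purpose of this exclusion.

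The cost is a few words in the SAP and minor programming on dosing and sampling dates that are already recorded. No study procedure changes.

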5.5.2. Immunogenicity

The antibodies to guselkumab will be summarized based on all participants who received at least one (complete or partial) administration of guselkumab and who had at least 1 sample obtained after their first administration of guselkumab (Section 4.7). Subjects will be analyzed according to the treatment groups that they actually receive. No imputation for missing concentration data will be performed.

The following analysis of antibodies to guselkumab will be performed by treatment group:

- Summary of antibodies to guselkumab status
- Summary of neutralizing antibodies to guselkumab status
- List of subjects positive for antibodies to guselkumab

In addition, to explore the relationship between antibodies to guselkumab status and serum guselkumab concentrations, efficacy and safety, the following analysis may be performed as appropriate:

- Summary of clinical response (e.g., ACR 20 and ACR50, IGA) by antibody to guselkumab Status
- Summary of injection-site reactions by antibody to guselkumab status
- Summary of serum guselkumab concentrations by antibody to guselkumab status
- Plots of median (IQ) trough serum guselkumab concentrations over time by antibody to guselkumab status.

5.5.3. Biomarker/Pharmacodynamic Analysis

Methods and results for biomarker/pharmacodynamic analyses will be presented in a separate technical report.

5.5.4. Pharmacokinetic/Pharmacodynamic Relationships

If data permit, the relationships between serum guselkumab concentration and efficacy may be analyzed graphically. If any visual trend is observed, a suitable population PK/PD model may be developed to describe the exposure-response relationship. Details will be given in a population PK/PD analysis plan and results of the population PK/PD analysis will be presented in a separate technical report.

5.5.5. Health Economics

In this study, Other Efficacy endpoints for health economics include the Work Productivity and Activity Impairment Questionnaire - Specific Health Problem (WPAI-SHP), a validated instrument that has been used to study the impact of various diseases on patients' ability to work and perform daily activities (http://www.reillyassociates.net/WPAI_General.html). The WPAI-PsA assesses the impact of PsA on work and other daily activities during the past 7 days. The WPAI-PsA consists of the following 6 questions:

Q1: currently employed (working for pay)? (yes, no) ***If No, skip to Q6.***

Q2: hours missed from work in the past 7 days due to PsA? (hours)

Q3: hours missed from work in the past 7 days due to other reasons? (hours)

Q4: hours actually worked in the past 7 days? (hours)

Q5: degree to which PsA affected work productivity while at work in the past 7 days? [0 (no effect) to 10 (completely prevented from working)]

Q6: degree to which PsA affected regular activities outside of work in the past 7 days? [0 (no effect) to 10 (completely prevented from daily activities)]

Based on the answers to the above 6 questions, 4 types of scores (in percentage) are calculated, with higher scores indicating greater impairment and less productivity, i.e., worse outcomes, as follows. **Note** that for participants with answer='No' to Q1, only the 4th score (ie., percent activity impairment outside work due to PsA) can be calculated.

1. **Percent work time missed** due to PsA (absenteeism): $100*Q2/(Q2+Q4)$
2. **Percent impairment while working** due to PsA (presenteeism): $100*Q5/10$
3. **Percent overall work impairment** due to PsA (combining absenteeism and presenteeism): $100*\{Q2/(Q2+Q4)+[(1-Q2/(Q2+Q4)) * (Q5/10)]\}$
4. **Percent activity impairment outside work** due to PsA: $100* Q6/10$

Change from baseline in WPAI scores measures the change in work productivity and/or activity impairment, where a positive change indicates a worsening and a negative change indicates an improvement.

The WPAI related Other Efficacy endpoints include:

- Change from baseline in **WPAI Percent Activity Impairment Outside of Work** scores by visit over time through Week 156.
- Change from baseline in **WPAI Percent Work Time Missed, Percent Impairment While Working, and Percent Overall Work Impairment** scores by visit over time through Week 156 among participants who were employed at baseline

Estimands

The same estimands defined in Section 5.3.6.1 will be used for WPAI.

Method of Analysis

The same methods of analysis for the Other Efficacy endpoints related to reduction of signs and symptoms and physical function in Section 5.3.6.2.10 will also be used for WPAI.

